ANODE v5.1, dd 14Jan2022

ANODE

Assessment of Natrox Oxygen DElivery

Prospective, multicentre, randomised controlled feasibility trial of the application of NATROX® topical oxygen therapy in patients with chronic and delayed healing foot ulcers.

Version 5.1, dd 14Jan2022

Chief Investigator's Statement of Ownership and Content.

I, [name], confirm that this protocol is my work and is owned by me. The protocol conforms with standards outlined in the Declaration of Helsinki 1964.
Name (PRINT):
Signature:
Date:

RESEARCH PROTOCOL SUMMARY

TITLE:	Prospective, multicentre, randomised controlled feasibility trial of the application of NATROX® topical oxygen therapy in patients with chronic and delayed healing foot ulcers.				
Short title:	ANODE study, Assessment of Natrox Oxygen DElivery				
IRAS number	262187				
Device description	The NATROX® oxygen wound therapy device is a battery-operated class II medical device licensed under Medical Device Directive 93/42/EEC. The 'box' contains the electrolysis-based oxygen generator and chargeable battery, and this is connected to the oxygen delivery system, a 'web' shaped applicator connected via a tube. In this manner 98% pure oxygen is supplied to the wound. The rate achieved is approximately 15 ml per hour. The web is placed on the wound and dressing is placed over it, and the device is then worn 24/7 by the patient.				
Study design	Prospective, multi-centre, randomised controlled feasibility trial				
Primary objective / outcome measures	To assess the feasibility of conducting a full RCT in the future - Participants' experience of and compliance with Natrox oxygen therapy - Recruitment and attrition rates, willingness of patients to consent and to be randomised, response rates to questionnaires, and degrees of missing data - Testing of eligibility criteria and ability/willingness of clinical staff to partake in recruitment and follow-up of participants - Adequacy of duration of follow-up (e.g. in relation to foot ulcer healing) - Appropriateness of inclusion/exclusion criteria and outcomes measures (both clinical and patient-reported). Descriptive assessment of wound size and characteristics (wk 0,3,6,9,12) Percentage 'wound healed' vs week 0 Percentage healing of the wound vs week 0 Change in semi-quantitative PUSH ulcer size score vs week 0 - SINBAD score (DFU only) vs week 0 - Wound closure status - Clinical characterisation of wound (erythema, purulence, odour, patient-reported pain) Safety of applied oxygen therapy in comparison to standard care arm (ongoing): - Wound infection incidence - Need for secondary interventions, such as surgery				
Secondary objectives / outcome measures					

	Patient-reported outcome measures (wk 0, 6, 12) - (Wound related) Quality of life scores (EQ-5D-5L and CWIQ) - Wound pain scale
Patient population	A total of 24 eligible participants will be randomised to receive either standard care or standard care plus Natrox topical oxygen therapy. Patients to be aged eighteen or over, with measurable foot ulcer present for at least two weeks, treated in podiatry clinic. Participants must have the capacity to provide informed written consent and complete patient reported outcome measures, and be willing and capable to wear the Natrox device.
	All participating patients – whose index wound has not healed by 50% or more in first four weeks of screening whilst in the study and under care of podiatry team - will be randomised for the trial phase. Those patients who were enrolled and whose foot ulcer healed 50% or more complete the study at the end of the four-week screening phase.
	In summary, of those participants whose wound does not heal 50% in four-week screening phase: - 12 Patient will receive treatment as usual (TaU) - 12 Patients will receive TaU plus adjunct Natrox topical oxygen therapy
	Randomisation will be stratified for ulcer size, with cut-off PUSH score of up to and including 5, and 6 and above.

1. LAY SUMMARY

Foot ulcers, which includes diabetic foot ulcers (DFU), can lead to infection and further deterioration to health. They are a considerable burden to both the NHS and the patient. The management of foot ulcers initially focuses on achieving wound healing. However, in many cases this objective is not met and chronic wound management then shifts its attention to avoiding infection and further complications. Clinicians have the option to treat the wound conservatively or more aggressively with oxygen. At present there is a lack of data available to aid clinicians in deciding what approach is best. The NATROX® oxygen wound therapy device is a licensed battery-operated class II medical device. The 'box' contains the electrolysis-based oxygen generator and chargeable battery, and this is connected to the oxygen delivery 'web' shaped applicator via a tube. The rate achieved is approximately 15 ml per hour. The web is placed on the wound and dressing is placed over it. In comparison to a spray or chamber, the Natrox system is portable and does not alter the frequency of clinical care required. Thus far, published data suggests that the Natrox device is capable of healing chronic delayed-healing foot wounds, typically present for over a year, by more than 50% over a treatment period of 8 weeks.

There are a few papers published on the use of and outcomes with the Natrox device in chronic foot ulcer patients, totalling circa 150 patients. However, there is a lack of evidence on how the device is perceived by patients who use it, i.e. acceptability of the device, and compliance rates. From a clinical perspective, more information is indicated to determine if, and how, wounds change in terms of bioburden (the microbiologic make-up of the wounds) as this may have implications if infection occurs in ulcers treated with Natrox. Finally, the effectiveness of Natrox needs to be evaluated in a randomised controlled trial setting.

In this feasibility trial, twenty-four patients, recruited from two NHS Trusts, will be enrolled in a randomised controlled trial. Participants will be eligible for randomisation to standard care or standard care plus adjunct Natrox oxygen therapy if their wound has not healed by at least 50% in the four weeks prior. In the trial phase, clinical (wound status) and patient-reported outcome measures will be collated at baseline, and periodically up to 12 weeks. Since this concerns a feasibility trial, the acceptability of the device, compliance with the therapy and study recruitment and retention rates will be assessed.

Since the Natrox device is already CE-marked, it can be incorporated in standard wound care practice across the UK without the need for regulatory delays and with minimal need for staff training. However, this is provided Natrox proves to be effective, safe, and cost-effective.

2. INTRODUCTION

The occurrence of foot ulcers has enormous cost complications. Figures available for diabetic foot ulcers (DFU) alone total £650 million per year once associated morbidity is taken into account (NHS Diabetes report). In the UK alone, 169,000 diabetic foot ulcers (DFU) occur every year (Guest et al, 2015). The International Diabetes Federation (2005) reported that up to 70% of all leg amputations happen to people with diabetes and 85% are preceded by a foot ulcer. Furthermore, three quarters of diabetics who experience an amputation will die within five years (Schofield et al, 2006). Diabetes NHS (2012) estimates total National Health Service (NHS) spending on ulceration and amputation in people with diabetes in England in 2010/11 was circa 0.7% of the budget and warned as diabetic numbers grow so will this expenditure. Lipsky et al (2004, 2012) associated infection in DFU with high mortality, high attendance at clinics and possible risk of amputation, advising antibiotics are required for infected wounds, but there is no evidence to support issuing antibiotics for uninfected ulcers. This is a critically important topic, since the longer that healing is delayed, the higher the risk of infection developing (Hampton and Collins, 2005; Grothier, 2015). To further illustrate the point concerning the impact of foot ulcers: the healing rate of DFUs is poor; on average, 24% of wounds have healed by week 12 of treatment, and only 31% at 20 weeks of treatment (Margolis, 1999). A cohort study involving 31 diabetic patients determined that the average healing time for neuropathic DFUs is 78 days whereas this increases to 133 days for patients with additional peripheral vascular disease (Zimny et al, 2002). Further analysis has shown that the size of the ulcer negatively correlates to the healing rate, whereas a patient's age, sex, or type of diabetes is not associated with a change in healing rate outcome (Oyibo, 2001). DFU healing progress at 4 weeks of treatment is a predictor of the likelihood that the wound will be healed by 12 weeks of treatment. If the wound has not healed by at least 50% after 4 weeks, the likelihood that the DFU will be completely healed by 12 weeks is reduced to circa 10% (Sheehan, 2003). Taken together, there is a major group of patients with DFU -those with larger ulcers, and co-morbidities, responding poorly to standard treatment in the first 4 weeks - that is at risk of ending up with long-term wounds taking over 3 months to heal, if at all. Therefore, enhancement of foot ulcer healing rate is desirable to minimise morbidity and healthcare costs.

Each year, the NHS spends approximately £2.3bn – £3.1bn (at 2005-2006 cost) on dressings and associated products, equating to 3% of the total estimated health expenditure (Posnett and Franks, 2008). Furthermore, patients with wounds cost the NHS up to £5 billion more per annum than matched control patients (Guest et al, 2015). Regarding dressing prescriptions, silver dressings represent one seventh of wound dressing prescriptions (Iheanado, 2010), resulting in a high cost implication for the NHS. Alternative approaches to accelerating the healing rate of DFUs may be beneficial not only from a patient perspective, but also in terms of reducing healthcare costs.

Oxygen is an essential component of the wound healing process (Hunt et al, 1969). Poor circulation due to diabetic angiopathy impairs the healing process and limits the degree of required growth factor release and angiogenesis (Falanga, 2005; Mathieu et al, 2006). Increasing oxygen levels can be achieved in various ways, including hyperbaric chamber treatment (Faglia, 1996). However, this method is costly, cumbersome and logistically challenging. An alternative is a porcine haemoglobin, Granulox, has shown initial promise but is derived from animals and needs to be applied numerous times per week in spray form (Arenberger et al, 2011; Norris, 2014; Hunt & Elg, 2016). The newly developed Natrox topical oxygen therapy device takes a different approach. It uses an electricity-

based oxygen generator, which then feeds oxygen through a tube and a 'web' onto the wound area (see Figure 1 and https://www.natroxwoundcare.com/). An initial pilot study on 10 chronic DFU wounds has shown promise; a median healing rate of 53% was achieved after eight-week long treatment with Natrox (Hayes et al, 2017). Similar results were achieved with a larger cohort of varying types of chronic wounds, including DFUs, venous leg ulcers, and arterial leg ulcers (Kaufman et al, 2018). The aim of this randomised, controlled, prospective clinical trial is to determine if the device is acceptable and feasible to introduce into foot ulcer treatment. Furthermore, the methodology applied in this initial study will be appraised for suitability in a larger trial setting. As a secondary objective, the efficacy of the Natrox topical oxygen therapy device as an adjunct therapy for foot ulcers will be assessed. The rationale behind including both diabetic and non-diabetic foot wounds is that the mechanism of action of Natrox is not affected by a patient's diabetes status and the product has shown promise in non-diabetic wounds (Kaufman et al, 2018).

3. INVESTIGATIONAL DEVICE

3.1 Introduction Natrox device

The Natrox® topical oxygen therapy device is a class II medical device licensed under Medical Device Directive 93/42/EEC. The system has two elements, namely the ; the Natrox® Oxygen Generator and the Natrox® Oxygen delivery system. The Natrox® generator is battery-operated and delivers 98% pure humidified oxygen to the wound bed at 13 ml/hour – oxygen is generated through water electrolysis. It is supplied with two rechargeable batteries and a charging kit. Since each battery will last for approximately 30 hours, users are advised to charge one battery whilst using the other and to change them over daily. The Natrox® oxygen delivery system is a sterile, single-use tube and 'web' that facilitates the wound interface. Due to the web design, wound exudate can escape and be absorbed by dressings without impairing the flow and diffusion of oxygen across the wound surface. The web is connected to the generator via a one meter long thin flexible tube. The Natrox® oxygen delivery system is to be changed at each dressing change in accordance with good clinical practice (it can stay in place for up to 7 days if clinically appropriate and indicated). Further information can be found at https://www.natroxwoundcare.com/ and please see paragraph below. If a patient wishes to get changed or have a shower then the oxygen delivery system can be temporarily disconnected from the oxygen generator. However, continues application of the device is indicated to achieve optimal therapy.

Figure 1, The Natrox topical oxygen therapy device

3.2 Medical Device management and staff training

The Natrox devices and related oxygen delivery systems will be stored in the podiatry clinic rooms or R&D office at the temperature and conditions recommended by the manufacturer. No requirement for involvement pharmacy or clinical trials pharmacist. Standard available stocks of dressings to be used as part of standard foot ulcer care.

The Natrox medical device will be managed as such:

- The suitably trained/delegated podiatrist will apply the Natrox device to the wound. This means both the 'web', the 'tubing' and the oxygen generating 'box'.
- Then the regular dressings will be applied, again by podiatrist (as per usual care)
- At the first study appointment, week 0, the patient will be explained how the box can be detached from the tubing/web, in order to allow patient to wash or change clothes.
- At this point, the patient must also be told to change the box every 24 hrs. The official Natrox instruction leaflet will be given to patient as an aide memoire.
- Patients must be seen in podiatry at least once every 7 days whilst they are in the trial, since the same web should not be on for longer than 7 days. This timing is in line with standard care.
- The web and tubing is replaced at this point. The replacement can take place sooner than after 7 days, if the dressing needs to be changed at that point anyway. Again, the podiatrist changes the web and tubing.
- At each clinic visit the patient is asked if they've experienced any issues with the device.

A team of podiatrists at both recruitment sites have been identified, see protocol summary pages 2-4, and they will be trained on the application and use of the Natrox device by a representative from Inotec AMD Limited. This person will also be available for any troubleshooting once the study is live. The podiatrists and research staff will also attend a site initiation visit on the ANODE study itself. For both sessions an attendance list will be circulated and signed by attending staff. All trained staff will then be added to delegation log for the ANODE study and be delegated the appropriate and relevant tasks in relation to study delivery.

4. STUDY HYPOTHESIS

4.1 **Primary objective**

To assess the feasibility of conducting a full RCT in the future.

4.2 Secondary objective

- To assess the acceptability and efficacy of the Natrox oxygen therapy device as an adjuvant therapy for foot ulcer healing

5. STUDY PROTOCOL

5.1 Study design and timeline

This concerns a multi-centre, controlled prospective randomized feasibility study. The study will be carried out in Cumbria by North Cumbria Integrated Care NHS Foundation Trust and South Tyneside & Sunderland Hospital NHS Foundation Trust. The study will take place in a local community setting with support and oversight from a senior podiatrist, the wider podiatry team and research staff. Research delivery staff will be delegated to provide support with data collection and processing. Table 1 outlines the planned timeline.

Table 1. Anticipated timeline

Month	Setup	Recruitment	Analysis	Finalise	
May-19	Submission for HRA approval				
July-19	HRA and Trust approval; NIHR portfolio adoption				
Oct-19		Start recruitment			
Jul-22		Finish recruitment			
Nov-22			Follow-up complete; Analyse data		
Dec-22				Manuscript report writing	&

5.2 Participant identification and research setting

Participants will be recruited from podiatry clinics and all eligible patients will be invited to take part until the required numbers have been achieved. Identification will be by the podiatrists who are supporting the study. A screening form will be completed for potentially eligible patients to confirm that they indeed meet the trial criteria.

The podiatry teams in Cumbria and South Tyneside will be supporting this study, and the study will take place in those localities. All research activity and also treatment as usual (ie application of dressings) will take place in these clinic settings.

To summarise, the podiatrists will:

- Identify potentially eligible patients and ask verbal consent for them being approached about the study by a member of the R&D team
- Complete the inclusion / exclusion criteria checklist on the screening form
- Treatment as usual activities (dressings, cleaning of wound, footwear advice), measure the wound size, take photos of wound, and complete the PUSH and SINBAD score once a patient has consented to taking part (informed consent will be taken by members of delegated R&D team, or one of the podiatrists as long as they are listed on the delegation log).
- Apply the Natrox device in accordance with manufacturer's instructions to suitably eligible participants.

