5.3 Consent

Those eligible will be approached and provided with an information pack and consent form, which will be signed to indicate that informed consent has been given. Patients will be given ample time to consider taking part, more than 24 hours if they wish. The direct healthcare professional will first approach a patient about the study, and after verbal consent by the patient the healthcare professional themselves or a member of the research team can go through the informed consent process. If there is insufficient time in clinic, the podiatrist or delegated research can follow-up with a phone call to the patient to ensure they understand the PIS and have had opportunity to ask any questions they may have.

The start of the 4-week screening period is the date of written consent being obtained.

Participants will receive no incentives and consent will be regarded as a process and not a one-off event. Participants are free to withdraw from the study at any time without the need to give any reasons for withdrawal. Their standard of care will not be affected by either declining to participate in the study or withdrawing during participation. Data collected up to the date of withdrawal will be retained for analysis. Only one questionnaire will be presented to patients who withdraw or complete early, the patient experience questionnaire (still voluntary for patients to complete or not).

5.4 **Recruitment**

Participants will be enrolled for a total of 16 weeks, see Table 2, or until ulcer healing has been achieved (if the latter occurs then they will still be followed up according to the study schedule in terms of patient-reported outcome measures). All participants will have demographic and medical data obtained and a number of baseline and follow-up measures.

Table 2. Overview of study measurements

Weeks	-4	0*	3*	6*	9#	12~
Clinical characterization of wound	Х	Х	Χ	Х	Х	Χ
Ulcer size (Coloplast grid or suitable equiv)	Χ	Χ	Χ	Χ	Χ	Χ
PUSH score	Χ	Χ	Χ	Χ	Χ	Χ
SINBAD DFU grading score (DFU only)	Χ	Χ	Χ	Χ	Χ	Χ
Wound status (closed/recurrence/infection)		Χ	Χ	Χ	Χ	Χ
photo of wound (if possible and consented by patient)		Χ		Х		Х
QoL CWIQ		Χ		Χ		Х
QoL EQ-5D-5L		Χ		Х		Χ
Experience questionnaire (Natrox only)						Χ

^{*} Up to 1 week early or late

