5.6 Outcome measures

5.6.1 **Primary outcome measures**

To assess the feasibility of conducting a full CRT in the future, the primary outcome measures are mainly:

Trial-related outcome measures

- Participants' compliance to and satisfaction with Natrox device
- Recruitment and attrition rates, willingness of patients to be consented and randomised, response rates to questionnaires, and degrees of missing data
- Testing of eligibility criteria and ability/willingness of clinical staff to partake in recruitment of participants
- Ability of sites and clinicians to recruit and randomise patients
- To assess any training requirements
- Adequacy of duration of follow-up (e.g. in relation to foot ulcer healing)
- Fitness for purpose of data collection methods including across and between care settings
- Suitability of inclusion/exclusion criteria and outcome measure tools.
- Adverse events

5.6.2 **Secondary outcome measures**

This study also aims to record wound characteristics and patient-related outcomes measures, as well as safety endpoints and microbiology assessments.

The main clinical outcome for this trial will be the efficacy of the Natrox oxygen therapy in terms of wound healing. For all participants, wound healing will be measured

Foot ulcer size, measured with wound grid tool (week -4, 0, 3, 6, 9, 12). Measured in % change in cm² - between week 0 and weeks, 3, 6, 9, and 12 respectively

Assessment wound size and characteristics (wk 0,3,6,9,12)

- Clinical characterisation of wound (incl. erythema, purulence, odour), wound closure status
- PUSH and, if applicable, SINBAD DFU score

Extended safety outcome measures, general and in relation to applied Natrox (ongoing):

- Wound infection incidence
- Need for secondary interventions (incl. need for surgery, admission to hospital, iv antibiotics)
- (indirect) reaction to Natrox, the web itself or oxygen therapy
- Any other adverse events

Patient-reported outcome measures (wk 0, 6, 12)

- Quality of life score (EQ-5D-5L and Cardiff Wound Impact Questionnaire)

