6. SUBJECTS

6.1 Anticipated number of research subjects

This concerns a feasibility trial, and therefore the results from this study should inform a potential effect size for Natrox oxygen therapy, and also the degree in variance in wound healing rates (primary clinical outcome). To date, there is not sufficient published data to gain an insight in the effect that Natrox may have on foot ulcer healing. Hayes et al (2017) previously conducted a pilot study involving 10 DFU patients. In that study, there was no screening phase and Natrox treatment lasted for eight weeks. At the week 8 time point, a mean healing vs baseline of 51% was achieved.

Guidance from a publication by Julious (2005) advises the use of 12 participants per treatment arm, and this approach will be taken here (see Table 3). Patient withdrawal rates before week 12 are not known at present and measuring this will be a primary aim

Table 3, sample size numbers required, based on hypothetical differences between published data and study outcomes

	Standard (control) arm	care	Standard care plus Natrox oxygen therapy arm
Patients (n)	12		12

Since this concerns a randomised controlled trial, albeit in the shape of a feasibility study, reprting will be done in line with CONSORT guidelines (Schulz, Altman & Moher 2010). The number of patients screened but who did not meet the inclusion criteria or who declined to participate will be recorded, as will any patients who are lost to follow-up (Appendix 2).

Since this study involves a screening period, after which patients may not qualify for Natrox intervention, it is anticipated that more than 20 patients will be recruited. The patient attrition rate (withdrawal and loss to follow-up) will also be recorded, since this involves a study with at multiple visits, albeit incorporated into standard clinical appointments. Patients will be recruited from the adult (age 18+) population routinely seen by the evaluating clinical staff members.

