8.2 Primary outcome statistics

The primary objective for this pilot study is the feasibility of conducting a larger scale randomised controlled trial. The secondary outcome statistics (on efficacy) will aid to inform the success of this pilot study and will therefore inform whether a larger scale trial is indicated. This will be based on signs of clinical effectiveness, positive patient feedback on the intervention, positive changes in foot ulcer related quality of life, recruitment to time and target, low attrition rates, minimal data queries and lack of or low number of adverse events. If the effect size of the Natrox intervention pedal is large enough, then this pilot trial may possibly provide a definitive answer concerning its clinical effectiveness.

The following descriptive statistics will be reported on:

- Number of patients screened
- Number of patients eligible/ineligible, and percentage of patients consented into the trial

Number of patients completed the trial/discontinued (plus reasons if discontinued)

Patient feedback on the use and comfort of the Natrox device, and compliance with the prescribed therapy regime will be summarised in tabular and graph format.

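### The screening form starts only after the podiatrist has made a first selection, so the eligibility counts can understate how many foot-ulcer patients the criteria remove and hide which criterion removes most

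*Protocol*

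**What the plan says.** Section 5.2 leaves the first selection to clinic staff: "Identification will be by the podiatrists who are supporting the study". The form follows that selection: "A screening form will be completed for potentially eligible patients to confirm that they indeed meet the trial criteria". The section then summarises the podiatrists' tasks in an unnumbered list. The first item is "Identify potentially eligible patients and ask verbal consent for them being approached about the study by a member of the R&D team" and the second is "Complete the inclusion / exclusion criteria checklist on the screening form".

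Section 5.3 gives a different order: "Those eligible will be approached and provided with an information pack and consent form". It also has the treating professional making the first approach.

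Section 6.1 promises that "The number of patients screened but who did not meet the inclusion criteria or who declined to participate will be recorded", with reporting in line with CONSORT.

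Section 5.6.1 lists among the primary outcomes "Testing of eligibility criteria and ability/willingness of clinical staff to partake in recruitment of participants", along with patients' willingness to consent and the suitability of the inclusion and exclusion criteria. The protocol summary does the same. Section 8.2 turns these into descriptive statistics: the number screened, and "Number of patients eligible/ineligible, and percentage of patients consented into the trial".

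**The concern.** In most trials it does no harm for a clinician to pick out likely candidates before any paperwork. Here the trial sets out to learn how the criteria perform, and the sift acts on that very quantity. Several exclusions in section 6.2.2 can be obvious to a podiatrist before a form is opened: an ulcer between the toes, a necrotic wound, an ulcer reaching bone, or a low ankle-brachial index already on file. If such patients are not regarded as potentially eligible, they leave no record. The ineligible count is then too small, and the recorded reasons lean towards criteria that are hard to see at a glance.

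There is a second, conditional worry about consent. If the verbal approach comes before the checklist, as the list in section 5.2 is ordered, a patient who refuses at that point may have no form. Unless such patients are counted as decliners under section 6.1, the percentage consented rests on people who had already shown some willingness.

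At stake is what the feasibility trial can tell the designers of a full trial about which criteria to relax, and what share of eligible patients will agree to take part.

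**Working it through.** **Plan's own figures.** The protocol states no expected eligibility or consent percentage, so there is none to reproduce. The only related count is the 24 to be randomised, which is 2 × 12 and does not bear on this point.

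**What the text fixes and leaves open.**
- *Who gets a form:* patients regarded as potentially eligible (5.2). No section provides a record of other foot-ulcer patients seen.
- *Who is counted as ineligible or declining:* patients who were screened (6.1). The protocol does not define that group. Section 5.2 uses the word for a form completed around identification; section 5.3 uses it for a four-week period that starts at written consent.
- *Order of approach and eligibility check:* approach listed first in 5.2, eligibility first in 5.3.
- *Denominators:* 8.2 gives counts of eligible and ineligible patients and one consent percentage with no stated denominator.

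**Eligibility, illustration on assumed rates.** Let e be the truly eligible share of foot-ulcer patients and f the share of ineligible patients set aside before a form. Assume every eligible patient gets a form. Then the eligible share of forms is e / (e + (1 − e)(1 − f)). Per 100 foot-ulcer patients:

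| e | f | Truly ineligible | Ineligible with a form | All forms | Eligible share of forms |
|---|---|---|---|---|---|
| 0.30 | 0 | 70 | 70 | 100 | 0.300 |
| 0.30 | 0.6 | 70 | 70 × 0.4 = 28 | 58 | 30/58 = 0.517 |
| 0.30 | 0.9 | 70 | 70 × 0.1 = 7 | 37 | 30/37 = 0.811 |
| 0.40 | 0.6 | 60 | 60 × 0.4 = 24 | 64 | 40/64 = 0.625 |
| 0.40 | 0.9 | 60 | 60 × 0.1 = 6 | 46 | 40/46 = 0.870 |

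On these inputs the forms show 6 to 28 ineligible patients where there are 60 to 70. As a description of all foot-ulcer patients, the eligible share is too high or, at f = 0, correct. It is not too low under this assumption.

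**Consent, illustration on assumed rates.** Let v be the share of eligible patients who agree to be approached, and c the share of those who then give written consent. Consent among all eligible patients is v × c. If first-approach refusers are left out, the reported figure is c.

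| v | c = 0.8: v × c | Excess (points) | c = 0.6: v × c | Excess (points) |
|---|---|---|---|---|
| 1.0 | 0.80 | 0 | 0.60 | 0 |
| 0.9 | 0.72 | 8 | 0.54 | 6 |
| 0.7 | 0.56 | 24 | 0.42 | 18 |
| 0.5 | 0.40 | 40 | 0.30 | 30 |

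If refusers are counted as decliners, the excess is 0 in every row.

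**Recruitment rate.** The number of patients consented or randomised per site per month uses no form-based denominator, so neither mechanism changes it.

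**The case against.** The strongest reply is that the text can be read generously. Potential eligibility is not defined and could take in almost anyone with a foot ulcer. Sections 6.1 and 8.2 both expect ineligible patients among those counted, so forms are evidently not kept for certain candidates only. Section 6.1 already commits to recording decliners, and neither the form nor the content of the flowcharts in the appendices is visible. All this stands as a reason to say that the counts *can* mislead, and no more. It does not remove the point: a form meant to confirm a prior judgement still omits those judged out, and the record promised in 6.1 covers only patients who were screened.

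A reader might infer that refusers of the first approach are certainly lost, because the checklist comes second in the 5.2 list. The documents do not support that: the list is an unnumbered summary and 5.3 puts eligibility first. A reader might also infer that the eligible share will come out near 100% whatever the criteria do. Section 8.2 lists counts rather than an eligible percentage, and even the assumed rates above give 52% to 87%. Nor does it follow that a full trial planned from this one would need more clinics or time than predicted, since that projection can rest on the observed recruitment rate.

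It may be said that denominators belong in a statistical analysis plan. Their definition may, but no such plan can recover patients for whom no record was started.

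**Conclusion.** The point holds in a limited form. As section 5.2 is written, the eligible and ineligible counts can understate how many foot-ulcer patients the criteria exclude, and can obscure which criterion does most of the excluding. That weakens a primary outcome. It rests on one assumption: that podiatrists set aside some plainly ineligible patients without starting a form, which the wording permits but does not state.

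The consent percentage may be overstated, on the further condition that first-approach refusers are not counted as decliners. The protocol does not settle this.

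The size of either effect cannot be computed from the documents. The ranges shown rest wholly on assumed rates and include zero. The observed recruitment rate per site is not affected. This is a cheap improvement to data capture, not a defect that invalidates the trial.

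**What to change.** In section 5.2, start the screening form as one anonymous line for every foot-ulcer patient seen by a participating podiatrist, before the verbal approach. The line records the first criterion failed (or none), whether the patient was approached, whether they agreed to be approached, and whether they consented. If continuous logging is too much, keep the log in fixed sample weeks at each site. Reword sections 5.2 and 5.3 so that they give the same order of eligibility check and approach.

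In section 8.2, report eligibility and reasons for ineligibility over all logged patients, and consent over all eligible patients, including those who refused the first approach.

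The cost is a revised form and a small amount of podiatrist time for patients who get no form today, with no extra visits or trial participants. The reported rates will look less favourable. Table 1 plans recruitment from October 2019 to July 2022 and this protocol version is dated January 2022, so on that timeline the log would cover only the remaining period. Its figures should be reported separately from the earlier counts.
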